## Publication Record

Version	Date	Primary Author	Description
Draft 1.0	14 June 2019	PPD	1 st Draft for GSK Review
Final 1.0	26 July 2019	PPD	Final version incorporating GSK comments/edits

## **ABBREVIATIONS**

ACIP: Advisory Committee on Immunization Practices

ACOG: American College of Obstetricians

ADaM: Analysis Data Model

AE: Adverse Event

ASD: Absolute Standardized Difference

BMI: Body mass index

CA: Congenital anomalies

CDISC: Clinical Data Interchange Standards Consortium

CI: Confidence interval

DMP: Data Management Plan

ED: Emergency Department

EDD: Estimated Date of Delivery

EHR: Electronic Health Record

GSK: GlaxoSmithKline

HIV: Human immunodeficiency virus

ICD: International Classification of Diseases

KPSC: Kaiser Permanente Southern California

MRN: Medical Record Number

PHI: Protected Health Information

PPROM: Preterm pre-labor rupture of membranes

PPV: Positive Predictive Value

R&E: Research and Evaluation

RR: Relative Risk

SAP: Statistical Analysis Plan

SAS: Statistical Analysis System

SDTM: Study Data Tabulation Module

SGA: Small for Gestational Age

SOP: Standard Operating Procedures

Tdap: Tetanus, diphtheria, acellular pertussis

## 1. INTRODUCTION

Whooping cough, also referred to as pertussis, is a highly contagious respiratory disease primarily caused by the bacterium *Bordetella pertussis*. The disease is most severe in unvaccinated or incompletely vaccinated young infants. To increase the protection of newborns, in October 2012, the Advisory Committee on Immunization Practices (ACIP) recommended tetanus-diphtheria-acellular pertussis (Tdap) vaccine to be administered during pregnancy to all pregnant women, regardless of whether they have received Tdap previously. The optimal timing for Tdap administration is between 27 and 36 weeks of gestation.

Two Tdap vaccines (Adacel and Boostrix) were licensed for use in the United States in 2005. These vaccines were recommended for routine use in non-pregnant adolescents and adults when introduced. Both Adacel and Boostrix can be used interchangeably. There are limited post-marketing safety data on Boostrix during pregnancy. Through partnership between Kaiser Permanente Southern California (KPSC) and the sponsor, GlaxoSmithKline (GSK), we will conduct an observational, electronic health record (EHR) database study to assess the safety of Boostrix following routine immunization of pregnant women in a community setting.

This Statistical Analysis Plan (SAP) provides a detailed description of the data considerations, statistical methods, data analysis and results presentation as previously proposed in the protocol and Data Management Plan (DMP), where applicable. The SAP also describes quality assurance procedures and analytic data format standards.

## 2. STUDY OBJECTIVE

### 2.1. Primary objective

To rule out a two-fold increase (non-inferiority testing) in the incidence of each of the following maternal and infant adverse events (AEs):

- Preeclampsia and/or eclampsia
- Intra-uterine infections such as chorioamnionitis and endometritis
- Small for gestational age (SGA)
- Preterm delivery

among women who were vaccinated with Boostrix on or after the 1st day of the 27th week of gestation as compared to the incidence in a historical cohort of pregnant women (approximately January 1, 2012 to December 31, 2013) who were unvaccinated with any Tdap vaccine throughout their pregnancy.

The null hypothesis and alternative hypothesis for test of relative risk (RR) are:

$$H_0: RR \geq 2$$

$$H_a: RR < 2$$

### 2.2. Secondary objective

1. To explore differences (superiority testing) in the incidence rate of other maternal and infant AEs, namely:
  - Post-partum hemorrhage
  - Poor fetal growth
  - Stillbirth/fetal death with or without congenital anomalies
  - Neonatal death (within 28 days of birth)
  - Maternal death (while pregnant or within 42 days of end of pregnancy)
  - Placental abruption
  - Preterm pre-labor rupture of membranes (PPROM)
  - Congenital anomalies (CA) at birth and through 6 months of age

between women who were vaccinated with Boostrix on or after the 1st day of the 27th week of gestation and a historical cohort of pregnant women (approximately January 1, 2012 to December 31, 2013) who were unvaccinated with any Tdap vaccine throughout their pregnancy.

The null hypothesis and alternative hypothesis for test of RR are:

$$H_0: RR = 1$$

$$H_a: RR \neq 1$$

2. To describe the incidence of maternal and infant AEs described above, as well as the incidence of spontaneous and therapeutic abortion with or without congenital anomalies, in pregnant women who were vaccinated with Boostrix before the 27th week of gestation.

### **3. STUDY DESIGN**

#### **3.1 Overview of study design**

This is an observational retrospective matched cohort study. The study will be conducted among pregnant women who are members of KPSC.

The exposed cohort (from the 27th week of gestation) will consist of pregnant women who received the Tdap vaccine (Boostrix) on or after the 1st day of the 27th week of pregnancy during the vaccination period at ob-gyn clinics of seven selected medical centers. Approximately 15,000 women vaccinated with Boostrix will be included in this study over approximately a one-year period from January 2018 to January 2019.

The unexposed cohort will consist of women, pregnant sometime during the approximate estimated period from 1/1/2012 to 12/31/2013 who never received Tdap vaccine during pregnancy. The unexposed cohort of pregnant women will be matched 1:1 to the exposed cohort of pregnant women for comparisons of maternal and infant AEs between the two cohorts.

Subject-level data will be collected for pregnant women and their infants through the EHR. For each individual pregnant woman, analytical follow up will begin on the date they receive the Boostrix vaccine, or the index date for the unvaccinated cohort, and will end on the date of

disenrollment or the end of pregnancy, whichever came first. For the maternal death endpoint, pregnant women will be followed for 42 days after the end of pregnancy. Infants born in KPSC hospitals will be followed for 6 months.

In addition, women vaccinated with Boostrix before the 27th week of gestation, with membership at the date of vaccination, and who were not vaccinated with any other Tdap vaccine at any other time during the pregnancy will be included for a descriptive analysis (single arm).

### **3.2 Study population, exposures, outcomes and covariates**

#### **3.2.1 Study populations/subgroups**

##### *Study population for main analysis (primary objective and secondary objective #1)*

- Pregnant women received prenatal care at KPSC
- Exposed cohort: vaccinated with Boostrix on the 1st day of the 27th week of pregnancy or later during the pregnancy and were not vaccinated with any other Tdap vaccine at any other time during the pregnancy or
- Unexposed cohort: pregnant at least one day during the approximate estimated period between 1/1/2012-12/31/2013 and did not receive any Tdap vaccine during the pregnancy
- Continuous membership (allowing up to a 31-day gap) between the 1st day of the 27th week of pregnancy and the index (vaccination) date

The unexposed cohort will be 1:1 matched to the exposed cohort on age at pregnancy start ( $\pm 1$  year), race/ethnicity (White, Black, Hispanic, Asian, and Other), and multiple gestation (yes/no). Every unexposed woman will be assigned an index date that is determined by the number of days from pregnancy start to the Boostrix vaccination date of her matched exposed woman. The same number of days calculated in the exposed woman will be added to the pregnancy start of the unexposed woman to determine her index date.

##### *Study population for descriptive analysis (secondary objective #2)*

- Pregnant women received prenatal care at KPSC
- Vaccinated with Boostrix before the 27th week of gestation and were not vaccinated with any other Tdap vaccine at any other time during the pregnancy
- Membership at the index (vaccination) date

##### *Subgroups for endpoint-specific analysis*

For some maternal and infant AEs (endpoints), additional restriction criteria will be applied. We will exclude individuals who do not meet the restriction criteria, but not the matched pair. Analysis will be conducted on a subgroup of the population:

- Small for gestational age (SGA): Infants 1) live born, 2) singleton, and 3) born in KPSC hospitals. Rationale: The evaluation of SGA is limited to singleton births because the reference values for SGA definition are established based on singleton births. The birth weight of infants born outside KPSC hospitals is not captured in claims, and such infants are therefore excluded for this endpoint.

- Preterm delivery: Pregnant women 1) with live birth and 2) with index (vaccination) date prior to 37 weeks gestation. Rationale: Pregnant women with an index (vaccination) date on or after 37th week of gestation are not at risk of preterm delivery, and are therefore excluded for this endpoint.
- Preterm pre-labor rupture of membranes (PPROM): Pregnant women with index (vaccination) date prior to 37 weeks gestation. Rationale: Pregnant women with an index (vaccination) date on or after 37th week of gestation are not at risk of PPROM, and are therefore excluded for this endpoint.
- Post-partum hemorrhage: Pregnant women with KPSC delivery. Rationale: Delivery information such as blood loss is not available for women who deliver outside KPSC, and such women are therefore excluded for this endpoint.
- Stillbirth/fetal death: Pregnant women with pregnancy outcome. Rationale: Pregnant women with unknown pregnancy outcome are considered as missing data, and are therefore excluded for this endpoint.
- Neonatal death (within 28 days of birth) and congenital anomalies at birth and through 6 months of age: Infants 1) live born and 2) born in KPSC hospitals. Rationale: Infants born outside KPSC hospitals may not be captured and may not be able to be linked back to their pregnant mothers, and are therefore excluded for this endpoint.

Analysis for preeclampsia and/or eclampsia, intra-uterine infections, poor fetal growth, placental abruption, and maternal death will be conducted on all pregnant women eligible for the main analysis and descriptive analysis.

### 3.2.2 Exposures

Boostrix vaccination will be received as part of routine clinical care. Vaccine exposure will be identified retrospectively from the electronic health records, including vaccine, manufacturer, and lot number entered at the time of vaccination.

### 3.2.3 Primary and secondary endpoints

Primary endpoints (Table 1) were selected based on their medical relevance, also considering the background incidence or prevalence of these endpoints.

Secondary endpoints (Table 1) were differentiated from primary endpoints to allow evaluation of the safety of maternal vaccination with sufficient statistical power on the primary endpoints, and to allow for hypothesis generation/signal detection on secondary endpoints.

Table 1. List of primary and secondary endpoints

Primary endpoints	Preeclampsia and/or eclampsia
	Intra-uterine infections such as chorioamnionitis and endometritis
	Small for gestational age (SGA)
	Preterm delivery
Secondary endpoints	Post-partum hemorrhage
	Poor fetal growth

Stillbirth/fetal death with or without congenital anomalies
Neonatal death (within 28 days of birth)
Maternal death (while pregnant or within 42 days of end of pregnancy)
Placental abruption
Preterm pre-labor rupture of membranes (PPROM)
Congenital anomalies at birth and through 6 months of age
Congenital anomalies of nervous system
Congenital anomalies of eye
Congenital anomalies of ear, face, or neck
Congenital anomalies of cardiovascular system
Congenital anomalies of respiratory system
Clefts
Congenital anomalies of upper gastrointestinal system
Congenital anomalies of lower gastrointestinal system
Congenital anomalies of genital organs
Congenital anomalies of renal system
Congenital anomalies of musculoskeletal system
Congenital anomalies of limb
Congenital anomalies of integument
Other and unspecified congenital anomalies
Spontaneous abortion with or without congenital anomalies (only for women exposed to Boostrix before the 27 th week of gestation)
Therapeutic abortion with or without congenital anomalies (only for women exposed to Boostrix before the 27 th week of gestation)

The algorithms for identification of primary and secondary endpoints are described in the DMP. Except SGA and preterm delivery, AEs identified through the algorithms will be chart reviewed to confirm the diagnosis and the onset (when applicable). Analyses of endpoints will be based on confirmed cases. For AEs with a chart-reviewed onset date, the event start date will be the onset date; for AEs without a chart-reviewed onset date (unknown or inapplicable), the event start date will be the earliest confirmed diagnosis date. To be a confirmed case, the event start date needs to be after the index date. Some AEs might be diagnosed during the delivery hospitalization, and have an event start date after the delivery date. For pre-eclampsia and/or eclampsia, intra-uterine infections, and poor fetal growth, the event date needs to be on or before the delivery date. For placental abruption and PPROM, if the event start date is after the delivery date, the delivery date will be used as the event start date.

SGA will be defined based on reference values derived by Talge et al. with a cut-off of <10th percentile (1). Talge et al used 2009-2010 US natality data and corrected for likely errors in gestational age dating to yield an up-to-date birth weight for gestational age reference. The

evaluation of SGA is limited to singleton births because the reference values for SGA definition are established based on singleton births.

Stillbirth/fetal death has a number of different and legally mandated definitions (2). This study will use ACOG's definition which defines stillbirth/fetal deaths at 20 completed weeks gestation or greater (if the gestational age is known). Maternal death will include all non-accidental deaths while pregnant or within 42 days of end of pregnancy. Neonatal death will include deaths within 28 days of birth among KPSC live born infants.

For a multiple gestation pregnancy, the pregnancy outcome will be recorded for each fetus, while the endpoint will be defined by the worst scenario. For examples, the woman will be considered to have a pre-term delivery, if any fetus was delivered pre-term after the index date. The woman will also be considered to have spontaneous abortion, therapeutic abortion, or stillbirth/fetal death if any fetus experienced these pregnancy outcomes after the index date.

For a multiple gestation pregnancy with multiple live births, only the infant(s) with infant AEs (neonatal death and congenital anomalies) will be chart reviewed. The endpoint will be defined at the infant level.

Additional birth outcomes will be captured among KPSC born infants for descriptive purposes, but will not be considered as AEs: birth length, head circumference, and Apgar scores.

### 3.2.4 Covariates

Covariates (Table 2) to be collected and explored include medical conditions indicative of a high-risk pregnancy and other relevant baseline characteristics. The algorithms for identification of high-risk medical conditions are described in the DMP.

Table 2. List of covariates (all covariates will be treated as categorical in the analyses)

High-risk medical condition
Thyroiditis (present/absent)
Diabetes (present/absent)
Other autoimmune diseases (present/absent)
Renal diseases(present/absent)
Cardiac diseases (present/absent)
Pre-pregnancy obesity (BMI>40: yes/no/missing)
Pre-existing hypertension (present/absent)
Rhesus sensitization (present/absent)
HIV infection (present/absent)
Syphilis infection (present/absent)
Cervical incompetence (present/absent)
Lifestyle factors
Smoking status from pregnancy start to index date (Yes/No)
Alcohol use from pregnancy start to index date (Yes/No)

Enrollment
Length of membership prior to 27 weeks gestation (but after pregnancy start) – having continuous membership from pregnancy start to index date (Yes/No)
Medicaid insurance (public health insurance: Indicator of low-income status) – any Medicaid enrollment from pregnancy start to index date (Yes/No)
Utilization
Health care utilization (receipt of medical care) from pregnancy start to index date
Any hospitalization or ED visit (Yes/No)
Number of outpatient visits (0-4/5-12/ $\geq 13$ )
Maternal Data
Number of previous pregnancies (0/1/ $\geq 2$ /Missing)
History of pregnancy loss (Yes/No)
Season of pregnancy start (September-March/April-August)
Vaccine
Receipt of other vaccines during pregnancy, e.g., influenza vaccine (Yes/No)
Receipt of vaccines containing diphtheria, tetanus toxoid or pertussis antigens within one year before pregnancy (Yes/No)
Matching variables
Race/Ethnicity (White/Black/Hispanic/Asian/Other)
Multiple gestation (Yes/No)
Age at pregnancy start (years)

Smoking status will be defined as current smoker or not. If patients reported they smoked any time from pregnancy start to index date, then they will be current smokers. Alcohol use will be defined in a similar fashion.

Length of membership prior to 27 weeks gestation (but after pregnancy start) will be defined as a dichotomous variable of having continuous membership (allowing up to a 31-day gap) from pregnancy start to index date.

Health care utilization will be defined as any hospitalization or emergency department (ED) visit, and number of outpatient visits (0-4, 5-12,  $\geq 13$ ) from pregnancy start to index date.

Receipt of other vaccines during pregnancy will be defined as any receipt of other vaccines from pregnancy start to index date.

The covariates included in adjusted analyses will be determined by scientific relevance, association with exposure and outcome, and data availability. Specifically, we will select covariates by following these steps:

1. The distribution of covariates will be reviewed. Those covariates in the same category with rare events will likely be combined as a single covariate. For example, we might consider grouping all chronic conditions into a single covariate.
2. The data availability will be checked. If a covariate contains a large proportion that is missing, and the proportion missing is differential by exposure, then the covariate may not be included.
3. Association of covariates with exposure will be assessed. We will use standardized difference to assess the balance of covariates between exposed and unexposed cohorts. Unlike p-values, for which magnitude is highly related to sample size, standardized difference is a unified approach to quantifying the magnitude of difference between groups regardless of sample size, where an absolute value less than 0.1 is considered a negligible difference (3). We will use a SAS macro %stddiff developed by PPD and PPD (4) to calculate the standardized differences for continuous and categorical variables. Potential confounders will be determined by absolute standardized difference (ASD)  $>0.1$ .
4. Association of potential confounders (identified from step 3) with each primary endpoint will be further assessed using a change-in-estimate approach (5). Diabetes, pre-existing hypertension (except for the analysis of the preeclampsia and/or eclampsia endpoint), Medicaid insurance, and health care utilization, which are considered as the most representative prognosis factors, will be kept in the adjusted model regardless of their association with exposure and primary endpoints. For a specific endpoint, the exposure coefficient estimate from a model adjusted for the 4 above covariates will be compared with the estimate from a model adjusted for one more covariate at a time. Covariates which result in a 10% change in the exposure coefficient estimate will be selected for final adjusted analysis.
5. All potential confounders (identified from step 3) will be included in the analyses of secondary endpoints. If the outcome is rare and the adjusted model cannot converge, problematic covariates will be removed from the model. If total counts from the two groups (i.e., sum of events in the exposed and unexposed cohorts) is less than 5, then no adjusted analysis will be performed.

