Health care utilization will be defined as any hospitalization or emergency department (ED) visit, and number of outpatient visits (0-4, 5-12,  $\geq 13$ ) from pregnancy start to index date.

Receipt of other vaccines during pregnancy will be defined as any receipt of other vaccines from pregnancy start to index date.

The covariates included in adjusted analyses will be determined by scientific relevance, association with exposure and outcome, and data availability. Specifically, we will select covariates by following these steps:

1. The distribution of covariates will be reviewed. Those covariates in the same category with rare events will likely be combined as a single covariate. For example, we might consider grouping all chronic conditions into a single covariate.
2. The data availability will be checked. If a covariate contains a large proportion that is missing, and the proportion missing is differential by exposure, then the covariate may not be included.
3. Association of covariates with exposure will be assessed. We will use standardized difference to assess the balance of covariates between exposed and unexposed cohorts. Unlike p-values, for which magnitude is highly related to sample size, standardized difference is a unified approach to quantifying the magnitude of difference between groups regardless of sample size, where an absolute value less than 0.1 is considered a negligible difference (3). We will use a SAS macro %stddiff developed by PPD and PPD (4) to calculate the standardized differences for continuous and categorical variables. Potential confounders will be determined by absolute standardized difference (ASD)  $>0.1$ .
4. Association of potential confounders (identified from step 3) with each primary endpoint will be further assessed using a change-in-estimate approach (5). Diabetes, pre-existing hypertension (except for the analysis of the preeclampsia and/or eclampsia endpoint), Medicaid insurance, and health care utilization, which are considered as the most representative prognosis factors, will be kept in the adjusted model regardless of their association with exposure and primary endpoints. For a specific endpoint, the exposure coefficient estimate from a model adjusted for the 4 above covariates will be compared with the estimate from a model adjusted for one more covariate at a time. Covariates which result in a 10% change in the exposure coefficient estimate will be selected for final adjusted analysis.

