##### 4.2 Analyses of primary endpoints

We will calculate crude incidence and 95% CI for each primary endpoint for the exposed and unexposed cohorts. Unadjusted and adjusted RR with two-sided 98.75% CI will be estimated comparing the exposed cohort to the unexposed cohort, accounting for multiple comparisons.

Analysis of primary endpoints will be used to evaluate the safety of Boostrix vaccination and concluded to be non-inferior if the upper limit of the 98.75% CI for the adjusted relative risk is below 2.

Analyses of preeclampsia and/or eclampsia and intra-uterine infection will be performed on all pregnant women eligible for main analysis. For events identified any time after the index date (e.g., preeclampsia and/or eclampsia and intra-uterine infection), the incidence will consist of the total number of women with the condition in the numerator and the total person time in the denominator. The person-year for a pregnant woman will be the time from the index date to the date of each adverse event, end of the pregnancy, or disenrollment, whichever comes first. The unadjusted and adjusted relative risk with 98.75% CI will be estimated by Poisson regression models accounting for the follow-up time without and with adjustment for potential confounders. If the outcome is common (i.e., incidence > 2%), a Poisson regression model with a robust error variance will be used to estimate the relative risk (6). The robust Poisson regression will be performed using the SAS Proc GENMOD procedure with the REPEATED statement subject= Patient\_ID.

Analysis of SGA will be performed on live singleton infants born in KPSC hospitals, while analysis of preterm delivery will be performed on pregnant women with live births, and with an index date prior to 37 weeks gestation. For events identified at delivery (e.g., SGA and preterm delivery), the incidence will consist of the total number of women or infants with the condition in the numerator and the number of women or infants for whom the condition can be assessed in the denominator. The unadjusted and adjusted relative risk with 98.75% CI will be estimated by Poisson regression models with robust error variances without and with adjustment for potential confounders. The planned methods of analysis by primary endpoint are outlined in Table 4. See Appendix A, Table Shell 4 for details.

Table 4. Analytic population and statistical methods by primary endpoint

Primary endpoints	Analytic population	Statistical Methods

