Preeclampsia and/or eclampsia	All pregnant women eligible for main analysis	Adjusted Poisson regression model accounting for follow up time, with robust variance estimate
Intra-uterine infections	All pregnant women eligible for main analysis	Adjusted Poisson regression model accounting for follow up time, with robust variance estimate
SGA	KPSC live born infant, singleton only*	Adjusted Poisson regression model, with robust variance estimate
Preterm delivery	Pregnant women with live birth, with index date prior to 37 weeks gestation	Adjusted Poisson regression model, with robust variance estimate

\*There are no well accepted SGA metrics for infants born to pregnant women with multiple gestation

Limiting analyses of endpoints to subgroups (e.g., KPSC live born infant) may cause matches to be broken, although we expect the proportions of non-live births and non-KPSC births to be small.

The matching variables will be included in the adjusted models of analyses of SGA and preterm delivery. Age at pregnancy start will be adjusted as a categorical variable (<24/25-34/≥35 years).

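### The adjusted preeclampsia/eclampsia and intra-uterine infection models leave out the matching variables, which can shift the decision RR by a few percent in either direction; including them costs almost nothing.

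*SAP*

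**What the plan says.** All references are to SAP Final 2.0, the current version.

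- **Matching (3.2.1).** "The unexposed cohort will be 1:1 matched to the exposed cohort on age at pregnancy start", and also on race/ethnicity and multiple gestation.
- **Forced covariates (3.2.4, step 4).** "Diabetes, pre-existing hypertension (except for the analysis of the preeclampsia and/or eclampsia endpoint), Medicaid insurance, and health care utilization" "will be kept in the adjusted model regardless of their association with exposure and primary endpoints". That is four items for intra-uterine infection and three for preeclampsia/eclampsia.
- **Other covariates (3.2.4, steps 3 and 4).** "Potential confounders will be determined by absolute standardized difference (ASD" with a cut-off of 0.1. Those that pass must then change the exposure coefficient by 10% relative to the base model: "the exposure coefficient estimate from a model adjusted for the 4 above covariates will be compared with the estimate" after adding one covariate.
- **Matching variables (4.2).** "The matching variables will be included in the adjusted models of analyses of SGA and preterm delivery". This follows a remark that restricting to subgroups may break matches. The age bands given are <24, 25-34 and ≥35.
- **Population and follow-up (4.2).** "Analyses of preeclampsia and/or eclampsia and intra-uterine infection will be performed on all pregnant women eligible for main analysis". "The person-year for a pregnant woman will be the time from the index date to the date of each adverse event", end of pregnancy or disenrollment.
- **Decision (4.2).** Non-inferiority is concluded when the upper 98.75% limit of the adjusted RR is below 2.

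**The concern.** The SAP appears to reason that the matching variables need to be in the model only where subgroup restriction breaks pairs. That holds for the unadjusted RR. It does not hold once other covariates enter.

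Matching makes age, race/ethnicity and multiple gestation independent of cohort overall, but not within levels of diabetes, Medicaid or visit count. If such a covariate is related to a matching factor and its frequency differs between the 2012-2013 and 2018-2019 cohorts, cohort and matching factor become associated within its levels. A model with the covariate but without the matching factor then gives a biased cohort effect.

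Nothing else in the model restores the matching: the robust variance in 4.2 clusters on patient, not on pair. The conditions are plausible. Protocol 4.1 chose the matching variables because such factors bear on pregnancy risk, and SAP 5.4 expects changes in health-seeking behaviour between the two periods. At stake is the validity of the decision statistic for two of the four primary endpoints.

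**Working it through.** **1. The plan's own figure.** Inputs from SAP 3.3: n = 15,000 per cohort, p0 = 0.01, p1 = 1.25 × 0.01 = 0.0125, margin R = 2, one-sided alpha = 2.5%/4 = 0.625% (z = 2.498). The score formula is

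power = Φ{[√n(R·p0 − p1) − z√v0]/√v1}.

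The constrained estimates under RR = 2 are 0.01499 and 0.00749, so v0 = 0.0445; v1 = 0.0519. Then (122.47 × 0.0075 − 2.498 × 0.2110)/0.2279 = 1.72 and power = 95.7%, as stated.

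**2. Can the matching variables enter?** They are not forced (step 4). Their standardized difference is about 0 by design, so they fail step 3. Section 4.2 adds them for SGA and preterm delivery only. No numbered step brings them into the other two models.

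**3. Size and sign with one covariate.** I fitted Poisson models to expected counts. From the documents: true RR 1.25 (SAP 3.3), baseline incidence 5.5% (unvaccinated chorioamnionitis rate in Protocol 1.1) and a matching factor M with prevalence 57.3% in both cohorts (Hispanic share, Protocol Table 1). Assumed, because the documents are silent: a covariate C with prevalence 25% in the unexposed and outcome RR 1.5, and an odds ratio of 3 between C and M unless stated.

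| C in exposed (standardized difference) | RR for M | Unadjusted | C only | C and M |
|---|---|---|---|---|
| 38.8% (+0.3) | 2.0 | 1.331 | 1.224 | 1.250 |
| 38.8% (+0.3) | 0.5 | 1.322 | 1.281 | 1.250 |
| 13.3% (−0.3) | 2.0 | 1.179 | 1.272 | 1.250 |
| 13.3% (−0.3) | 0.5 | 1.192 | 1.226 | 1.250 |
| 29.4% (+0.1) | 2.0 | 1.276 | 1.242 | 1.250 |
| 25% (0) | any | 1.250 | 1.250 | 1.250 |
| 38.8% (+0.3), C and M unrelated | 2.0 | 1.327 | 1.250 | 1.250 |

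The first row shows the mechanism. M is 57.3% in both cohorts overall. Among women with C it is 75.8% in the unexposed and 73.0% in the exposed; among women without C it is 51.1% and 47.4%. The range is 1.224/1.25 = 0.979 to 1.281/1.25 = 1.025, that is −2.1% to +2.5%.

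**4. Several covariates together.** True RR 1.00; age 36 and over 16% and Black 8.3% (Protocol Tables 1 and 2, age at vaccination). Assumed: multiples 2%; outcome RRs of 1.4, 1.6 and 3.0 for older age, Black race and multiples; era shifts of Medicaid 7 to 13%, 13 or more visits 28 to 38%, diabetes 12 to 15%, hospital/ED use 26 to 32%; covariate outcome RRs of 1.2 to 1.5. Pre-existing hypertension was not modelled. With odds ratios of 1.5, 2 and 3 between covariates and matching factors, the planned model gave 0.985, 0.974 and 0.960. With no association it gave 1.000, and with covariates falling instead of rising 1.025. Half the shift gave 0.979 to 0.993. Double gave 0.925 to 0.971, but that implies standardized differences of 0.36 for Medicaid and 0.42 for visits. Adding the matching variables returned 1.000 every time.

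**5. Effect on the decision.** SE(log RR) = √[(1−p0)/(n·p0) + (1−p1)/(n·p1)].

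- True RR 1.25: the expected upper limit is 1.25 × exp(2.498 × 0.0453) = 1.40 at 5.5% incidence, and 1.34 to 1.46 with a shift of −4% to +4%. At 1% incidence (SE 0.109) it is 1.64, and 1.58 to 1.71.
- True RR exactly 2, 5.5% incidence (SE 0.0410): one-sided error is Φ(−2.498 − ln(shift)/SE). A −2% shift raises it from 0.625% to 2.2%; +2% lowers it to 0.14%. At 1% incidence (SE 0.0993) the figures are 1.1% and 0.35%.

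**The case against.** A reader might infer that adjustment over-corrects and pulls both RRs downward, which would favour the non-inferiority claim. The documents do not support that. The sign depends on the direction of each covariate's shift between periods, its association with the matching factors, and the effect of those factors on each outcome. None is given, and the two endpoints may differ. Of the seven rows above, three shift downward, two upward and two not at all.

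The strongest case on the other side is that this hardly matters. The design already allows a bias of 1.25 against a margin of 2, and in the examples the planned adjustment usually lands nearer the truth than the unadjusted RR. At 5.5% incidence a shift of this size leaves the probability of concluding non-inferiority essentially unchanged up to a true RR of 1.5. It begins to matter from about 1.6 to 2, or somewhat sooner at lower incidence. Unadjusted and adjusted RRs are both reported. This stands and keeps the severity low.

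It can also be said that Table 2 lists the matching variables as covariates, that selection mentions scientific relevance, and that no text excludes them. True, but the SAP then sets out specific steps, and none admits them. At best the models are ambiguous.

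A reader might also carry the finding over to poor fetal growth and placental abruption. Those models follow step 5, without the forced covariates, and no bias was computed for them. Finally, pairs are intact only at entry, since person-time ends individually.

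**Conclusion.** The gap is real and small. By the SAP's own steps, the adjusted models for preeclampsia/eclampsia and intra-uterine infection contain covariates that may be related to the matching factors but not the matching factors themselves. The adjusted RR can then be biased even though every eligible woman is analysed. The bias is downward if the covariates became more common and the matching factors raise risk, upward if one of those signs is reversed, and nil if the covariates are balanced or unrelated to the matching factors (taking covariate and factor as positively related). Its size, about 1% to 4%, rests wholly on assumed imbalances and associations. It is unlikely to reverse a conclusion when the true RR is near 1 to 1.25; near the margin it would move the nominal error up or down. Low severity, but a free improvement.

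**What to change.** In SAP 4.2, extend the sentence on matching variables so that age band, race/ethnicity and multiple gestation are in the adjusted models for all four primary endpoints (multiple gestation is constant for SGA, which is singleton only). In 3.2.4 step 4, put them in the base model, and state that this base has three forced covariates for preeclampsia/eclampsia and four otherwise. Correct the age bands, since <24/25-34/≥35 leave age 24 without a category. The same sentence can cover poor fetal growth and placental abruption when step 3 covariates are added there.

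The cost is about 7 parameters: 2 for age, 4 for race/ethnicity, 1 for multiple gestation. All are already in SAP Table 2. At 2% incidence, 30,000 women give 600 events, so the loss of precision should be negligible.
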